6 STUDY INTERVENTION

6.1 STUDY INTERVENTION(S) ADMINISTRATION

6.1.1 STUDY INTERVENTION DESCRIPTION

Intervention Clinics/Patients: The CKD-CDS intervention provides updated clinical recommendations at any primary care visit for study-eligible patients; at intervention clinics these are seen by PCPs and patients as described. At usual care clinics, the CDS output is not displayed or accessible to PCPs or patients but is archived electronically for analysis purposes. The CDS presents to patients and their PCP an evolving array of timely, evidence-based treatment options to improve CKD care (see Figure 2 below). Treatment options are patient specific, tailored to the patient's current clinical state, and evolve over time as the patient's clinical state evolves, or when evidence-based guidelines evolve. As described in detail above, the CKD-CDS intervention proposed in this project is rooted in a series of antecedent studies that developed more limited but successful forms of CDS.^{40, 63, 64} From an operational point of view, implementing CKD-CDS at intervention clinics requires a series of 4 distinct steps that occur at every encounter as described in Figure 2 below.

Step 1: Data exchange and evaluation: The EHR securely exchanges data with the Web Service at every encounter of patients aged 18-75 triggered by BP entry or chart opening for video and phone visits.

Step 2: Recognition of CKD and presence of care deficits: Patients with stage 3-4 CKD are automatically identified by the Web Service and evaluated using algorithms maintained in the Web service for identification of CKD and for the 5 emphasized care gaps (identification of CKD, BP control, glucose control, ACEI/ARB use if appropriate, , and nephrology consultation if appropriate). If the patient has a care gap, the rooming staff receives an immediate BPA prompt to print CDS materials for the patient and the provider to review and use for shared decision making. Using a sequence of steps successfully implemented in previous studies, the rooming staff will print the materials and give the lay version to the patient to review while waiting for the provider. A professional version is left on the door for the provider to review before entering the exam room. This approach has been well-liked by our providers to help them be prepared and to engage patients in their care needs before the clinician-patient interaction. PCPs can also optionally view an electronic version of the CDS materials. The CDS can be viewed in real time for any patient by clicking on a button programmed in the EHR encounter display.

Step 3: Use of CKD-CDS recommendations as shared decision-making tools: The participating providers and all rooming staff in the intervention clinics will be trained in the use of the provider (professional) and patient (low-literacy) versions of the CKD-CDS. For this study, the CDS tool will be adapted to emphasize CKD and, for each identified deficit in CKD care, the CKD-CDS will display patient-specific recommendations consistent with then-current national CKD clinical guidelines; for example: (a) recognize CKD and ask the PCP to enter a CKD diagnosis on the problem list if indicated, and/or (b) specific considerations for how to modify BP control, glucose control, or ACEI/ARB therapy, and/or (c) refer certain patients to nephrology when referral criteria are met. The PCP assesses patient preference for any of the CKD-related treatment options. If the patient wants to act on 1 or more, the PCP can address it then or schedule a subsequent visit for that purpose. If the patient is not interested in any

option, no further action is needed at that day's visit. The decision support provided to the PCP is very specific and, if pharmacotherapy is indicated, decision support specifies either initiation or titration of specific drugs based on the drugs/doses the patient is currently taking, distance from goal, and other clinical considerations outlined above. The patient version of the CKD-CDS uses symbols to provide easy patient recognition of priority clinical areas and then suggests potential treatment options they can discuss with their provider. Presenting key CKD care recommendations when indicated (all of which are evidence based and capable of improving CKD care) allows the patient freedom to select his or her preferred treatment option from among several evidence-based potentially beneficial treatment options. Because patient preference for health-related actions varies across specific actions, offering several options improves the chance that a given patient may be interested in addressing at least 1 of the evidence-based options presented. Moreover, patient engagement is a key predictor of subsequent adherence and success of treatment, as we have previously shown in this patient population.⁶⁵⁻⁷⁰ It is important to realize that the printed page the patient receives *is designed to direct discussion to a set of prioritized evidence-based treatment options with likely benefit to that patient.

Step 4. Take action based on the decisions made: After discussing with the patient, the provider can then go ahead and order the recommendations suggested by the CDS such as labs, medication, e-consults or referrals to nephrology or other specialists. All actions taken are governed by the provider's clinical judgement and the patient's preferences, not by the CKD-CDS.

Usual Care Clinics: All control clinics/patients will continue to use the basic EMR-linked CDS for CV risk factor management. This CDS system includes algorithmically derived identification of high CV risk patients and prioritized treatment suggestions for lipids, BP, glycemic control, weight, tobacco, and aspirin use based on distance from goal, current medications, comorbid conditions, labs, allergies, and safety considerations.⁷¹⁻⁷⁶ The basic CDS does not include information specific to CKD care. Important to note is that the CKD-CDS tool will be running silently (in the background) at all clinics randomized to the Usual Care arm of the study. However, only the results of algorithms run by the basic EMR-linked CDS for CV risk factor management will be displayed in the Usual Care clinics. Running CKD-CDS silently in Usual Care clinics ensures that identification of study-eligible patients, and collection of primary outcome data will be done identically across all randomized clinics. Our ability to control the display of the CKD-CDS tool by clinic ensures that patients in Usual Care clinics continue to receive current standard of care (CDS for CV risk) and prevents intervention contamination at Usual Care clinic visits.

6.1.2 DOSING AND ADMINISTRATION

Not applicable

6.2 PREPARATION/HANDLING/STORAGE/ACCOUNTABILITY

6.2.1 ACQUISITION AND ACCOUNTABILITY

Not applicable

6.2.2 FORMULATION, APPEARANCE, PACKAGING, AND LABELING

Not applicable

6.2.3 PRODUCT STORAGE AND STABILITY

Not applicable

6.2.4 PREPARATION

Not applicable

6.3 MEASURES TO MINIMIZE BIAS

The information exchange between the web service and electronic health record occurs automatically at each visit at the randomized clinics. Algorithms use the information extracted from the electronic health record to systematically assess care gaps, treatment opportunities and safety issues, and then assemble tailored intervention content that incorporates algorithm outputs. As a result, the intervention content made available to front end users is up to date, informed by all available and relevant data and consistent with treatment guidelines across all patients and encounters.

6.4 STUDY INTERVENTION COMPLIANCE

Achieving and maintaining high CKD-CDS use rates. The intervention relied on nursing staff rather than providers to print the CDS tools when a best practice advisory (BPA) pops up during the rooming process for patients who meet the study eligibility criteria. We set a goal with providers and clinics staff to print the CDS tools at 75% or more of eligible encounters and sent clinic leaders frequent reports of clinic and provider CDS print rates. We used outreach phone calls/emails to clinic leaders if print rates drop below goal.

PCP and clinic staff training. All training activities for intervention clinics were conducted collaboratively with HealthPartners and Park Nicollet, and the research team. We conducted training sessions either in-person or through live or taped webinars. Training focused on workflow and enhancements made to the existing CDS to address CKD. Training was modeled after successful training programs conducted in previous studies. We also provided information about the study and interventions in online newsletters and communications.

Mechanisms for collecting ongoing feedback from PCPs. Once the CKD-CDS tool was implemented in the intervention clinics, PCPs or clinic staff with questions or concerns about any of the recommendations that display for an individual patient, were able to provide immediate feedback to the research team through a tab on the online CDS display or through emailing the study team. The feedback was sent automatically through an encrypted email to the research staff for triage. This process was used infrequently but was useful to identify and correct minor coding bugs, especially during the pilot phase. It also enabled research team clinicians to answer questions for providers who were confused or not knowledgeable about current evidence-based CKD care recommendations. The research team provided a timely response to all providers who send feedback. The process was quite useful as a way to improve the accuracy of the CDS and to educate individual providers as needed.

6.5 CONCOMITANT THERAPY

Not applicable

6.5.1 RESCUE MEDICINE

Not applicable

7 STUDY INTERVENTION DISCONTINUATION AND PARTICIPANT DISCONTINUATION/WITHDRAWAL

7.1 DISCONTINUATION OF STUDY INTERVENTION

This minimal risk study did not include specific halting rules. The CDS suggestions were evidence-based and guideline driven and providers are always advised to exercise their clinical judgement with any CDS suggestions. However, safety monitoring meetings were held regularly to assess frequency of possible adverse events related to overtreatment (severe hypoglycemia, documented hypotension, abnormal potassium values, etc.) in all randomized clinics.

7.2 PARTICIPANT DISCONTINUATION/WITHDRAWAL FROM THE STUDY

Providers and patients exposed to the clinical decision support can ignore or disregard any component of the intervention at their discretion.

Patients who opt-out of participating in research were excluded from outcomes analyses.

7.3 LOST TO FOLLOW-UP

Unless they opted out of research, all patients who met study eligibility criteria and had an index visit in the accrual period were eligible for inclusion in the analysis; inclusion in specific outcome analyses varied by the clinical care gaps that were present at the index visit.

8 STUDY ASSESSMENTS AND PROCEDURES

8.1 EFFICACY ASSESSMENTS

The data used to evaluate the effectiveness of CKD-CDS system on reducing 5 CKD care gaps will derive from the CKD-CDS tool itself (e.g., care gaps present at index visit) or the electronic health record (e.g., CKD diagnosis, ACEI / ARB orders). There are no scheduled assessment visits from accrued patients. Rather, data elements that document study eligibility and care gaps at the index visit, and outcome events that occur in the 18 months following the index visit, will be recorded in these electronic resources as care is delivered to patients, with the timing of care delivery driven by clinician and patient judgment. This clinic-based pragmatic trial will not direct the timing, manner or amount of care delivered to any accrued patient according to a pre-defined schedule.

8.2 SAFETY AND OTHER ASSESSMENTS

The CDS tool uses patient information in the electronic health record to apply evidence-based methods to identify eligible patients, compute CV risks, prioritize CV risk reduction, compute medication adherence, identify results of adherence assessments and action plans, and provide treatment recommendations based on a complex set of evidence-based algorithms. The study team has extensive experience in health services research and clinical research with human subjects, with procedures to safeguard privacy and personal information. See section 10.1.3 below on a detailed description of procedures put in place to assess and ensure safety of patient information.

Intervention adherence, defined as the rates at which CKD-CDS was opened and printed at study-eligible visits, was measured and monitored continuously during the study period and reported monthly to clinic leadership, as described above, despite a 6 month disruption due to the Covid-19 pandemic.

We used passive surveillance of electronic health record and administrative data sources maintained by HealthPartners to monitor the occurrence of safety events. These events included hypotension, hypoglycemia, electrolyte disturbances, emergency department visits, inpatient admissions for renal and non-renal causes, major cardiovascular events and mortality. Benefits to this approach are that safety events were ascertained identically for all accrued patients in all randomized clinics.

Documentation of the safety events occurred in the course of delivering health care, ensuring that records are reasonably accurate and complete with minimal and randomly missing information. Missing information due to events for which patients do not seek care or care that escapes documentation in the EHR was assumed to occur rarely and equally across treatment groups.

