8.3.4 TIME PERIOD AND FREQUENCY FOR EVENT ASSESSMENT AND FOLLOW-UP

We accessed the electronic health records and administrative data of all patients who accrued to this pragmatic trial in the course of preparing for regularly scheduled data safety monitoring meetings. We extracted data elements that documented the occurrence of any of the safety events (e.g., diagnosis codes, laboratory value, admission records) between 12 months prior to each accrued patient’s index visit and 18 months after the index visit of the last-accrued patient. The rates at which each event occurred (e.g., events per 100 patient-years) were calculated in the pre- and post-index periods by randomized treatment group so that differential changes in event rates might be observed. Event rate summaries were presented at data safety monitoring meetings approximately thrice-yearly. By their very nature, the occurrence of these safety events had been documented by health care professionals in the course of delivering timely treatment and appropriate follow-up to the accrued patients.

The occurrence of an AE or serious adverse event (SAE) may also come to the attention of project team members during patient and provider survey results. These AEs not meeting the criteria for SAEs will be captured on the appropriate report forms. Information to be collected includes event description, time of onset, clinician’s assessment of severity, relationship to study procedures (assessed only by those with the training and authority to make a diagnosis), and time of resolution/stabilization of the event. All AEs occurring while on study will be documented appropriately regardless of relationship. All AEs will be followed to adequate resolution.

Changes in the severity of an AE will be documented to allow an assessment of the duration of the event at each level of severity. AEs characterized as intermittent require documentation of onset and duration of each episode.

The project manager, in collaboration with the PI will record all reportable events with start dates occurring any time after inclusion into the study population until 7 (for non-serious AEs) or 30 days (for SAEs) after the last day of study participation. Events will be followed for outcome information until resolution or stabilization.

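### Section 8.2 says safety events are ascertained identically in both arms, but only the extraction is identical; lab- and code-based events may be recorded more often in the intervention arm, and the planned rates cannot separate detection from harm.

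*Combined protocol and SAP*

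**What the plan says.** Section 8.2: "We used passive surveillance of electronic health record and administrative data sources maintained by HealthPartners to monitor the occurrence of safety events". The list is mixed: "These events included hypotension, hypoglycemia, electrolyte disturbances, emergency department visits, inpatient admissions for renal and non-renal causes, major cardiovascular events and mortality". Section 8.2 then makes the claim at issue, "Benefits to this approach are that safety events were ascertained identically for all accrued patients in all randomized clinics", and adds that missing information from events for which no care is sought, or from "care that escapes documentation in the EHR was assumed to occur rarely and equally across treatment groups".

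Section 8.3.4 says how events are found: the team extracted "data elements that documented the occurrence of any of the safety events (e.g., diagnosis codes, laboratory value, admission records"). Event rates, with events per 100 patient-years as the example unit, are calculated before and after the index visit by arm. Section 10.1.6 compares monitored rates between arms and requires significant differences to be reported to the NIH and the IRB. Section 9.4.4 adds no analysis detail.

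The intervention is described in 6.1.1. In Step 3 the tool may "ask the PCP to enter a CKD diagnosis on the problem list if indicated". In Step 4 the provider can "order the recommendations suggested by the CDS such as labs, medication, e-consults or referrals to nephrology or other specialists". Under the same heading, the usual-care tool is said to carry no CKD-specific content.

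**The concern.** Applying one extraction to every clinic makes the handling of recorded data equal. It does not make the chance that an event gets recorded equal. An electrolyte disturbance appears only if a sample was drawn, and a diagnosis-coded event only if someone entered the code. The intervention is aimed at part of that recording process and reaches one arm only. More CKD documentation and more nephrology referral are primary endpoints 1 and 5. The plan thus hopes for a difference between arms in coding and referral for efficacy, while assuming equal documentation for safety.

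At stake is the reading of an excess. If the intervention arm shows more abnormal potassium values, the safety officer needs to know whether more patients were harmed or more were tested. The plan states no testing rate by arm, no rate per patient tested, no definition of a renal admission, and no sensitivity analysis for detection.

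**Working it through.** The documents give no figure for safety ascertainment, so there is none to reproduce. I set the relevant sections side by side, checked the planning inputs I borrow, and then worked through the mechanism with assumed inputs.

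**1. The route from intervention to record**
- 8.1: there are no scheduled assessment visits in either arm.
- 8.3.4: events come from codes, laboratory values and admission records.
- 6.1.1: prompts for CKD coding, and suggested labs and referrals, are shown in intervention clinics only.
- 6.1.1, Step 4: every action remains at the discretion of provider and patient.

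The route exists. Its strength is not stated.

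**2. Borrowed planning inputs (9.2, Table 2)**
- N: 5,766 × 30/17 = 10,175, as stated.
- Design effect = 1 + (10,175/30 − 1) × ICC, which is 4.38 at ICC .01 and 17.91 at ICC .05. Effective N is 2,322 and 568.
- Detectable H1 difference at 80% power, two-sided 0.05: 5.80 points (base 50%, ICC .01) and 11.15 points (base 60%, ICC .05). Table 2 gives 5.8-11.1.

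**3. Lab-detected events** (assumed: equal true risk, testing unrelated to risk, constant yield per test)

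Recorded rate = testing rate × yield per test. With equal yield, the spurious ratio is the ratio of testing rates:
- 10%, 25% or 50% more tests: 1.10, 1.25 or 1.50
- equal testing: 1.00

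The same holds for the proportion of patients tested. For 50% against 55, 60, 65 or 70%, the ratio is 1.10, 1.20, 1.30 or 1.40. If the extra tests fall on lower-risk patients, the ratio is smaller.

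**4. Could this produce a nominally significant difference?** (assumed: true rate 10% in both arms, 50% against 60% tested)

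Recorded rates are 0.10 × 0.50 = 5.0% and 0.10 × 0.60 = 6.0%. With 10,175/design effect/2 patients per arm, the chance of a two-sided p below 0.05 is 0.60 at ICC 0, 0.48 at ICC .001 and 0.18 at ICC .01. The plan sets no alpha or ICC for safety, so these are illustrations.

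**5. Does the pre/post comparison remove it?** (assumed testing proportions)

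Usual care: 60% tested before and after. Intervention: 60% before, 70% after. Ratio of rate ratios = (0.70/0.60) / (0.60/0.60) = 1.17 with no harm. The detection difference starts at the index visit in one arm, so the contrast keeps it.

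**6. Renal-cause admissions** (label undefined; assumed 3% truly renal and 17% other admissions per arm)

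Labelled renal = 3% + 17% × m × c, where c is the share with CKD coded and m is the chance that another admission of a CKD-coded patient is labelled renal. I take c = 50% under usual care against 55.8, 61.1 or 70% (Table 2's 50% base plus 5.8, 11.1 or 20 points).

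| Labelling rule | Ratio at 55.8 / 61.1 / 70% |
|---|---|
| Principal cause only (m = 0) | 1.00 / 1.00 / 1.00 |
| m = 0.10 | 1.03 / 1.05 / 1.09 |
| Any CKD code (m = 1) | 1.09 / 1.16 / 1.30 |

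The extreme case, in which an admission counts as renal only if CKD is charted, gives (50 + 20)/50 = 1.40 or (60 + 20)/60 = 1.33 for the full 20-point gain. All-cause admissions are unchanged throughout.

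**The case against.** The best reply is that 8.2 describes the surveillance method, which is the same in both arms, and that its next paragraph openly states the equal-missingness assumption. Labs appear only as an example in Step 4, with no prompted panel and no testing rates. Action is discretionary, and the display was off from March to August 2020 (4.2). In-person data exchange is triggered by BP entry and the tool runs silently in usual care (6.1.1), so BP readings per in-person visit are not shown to differ. Usual care also has decision support for BP and glucose. Mortality, major CV events and ED visits are already monitored, 9.4.2.1 already lists admissions and ED visits by arm without a cause split, and no primary conclusion rests on this.

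Most of that stands, and it limits the point. A reader might infer that events will be recorded more often in the intervention arm without any extra harm. The documents do not support that: the extra testing is not quantified, and Steps 3 and 4 cover drug treatment as well as labs, so real events could rise too. A reader might also infer that neither an excess nor its absence can be interpreted. That goes too far: if the bias in lab events runs toward apparent harm, finding no excess is more reassuring. Section 10.1.6 requires significant differences to be reported; it does not say they must be labelled as harm.

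What the reply does not answer is that equal missingness is assumed rather than checked, and that the planned rates cannot attribute an excess to testing or to harm.

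**Conclusion.** The point holds in limited form. Identical ascertainment is supported for extraction and unsupported for detection. Lab-detected events may be over-recorded in the intervention arm, as may renal-cause admissions if the label uses CKD or problem-list codes; non-renal admissions would then move the opposite way. True harm may contribute as well, and the plan offers no way to separate the two.

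The size cannot be fixed from the documents. The 1.1-1.5 range for lab events rests on an assumed 10-50% increase in testing, unrelated to risk and with constant yield; with equal testing the bias is nil. The 1.33-1.40 for renal admissions is the upper end on Table 2's base rates and needs both the extreme label and the full 20-point gain; a principal-cause label gives 1.00. Mortality and all-cause admissions and ED visits depend little on this route. This is an inexpensive improvement to the safety comparison, not a threat to the primary analyses.

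**What to change.** 1. In 8.2, say that extraction was identical in all clinics, and drop the untested statement that undocumented events are rare and equal across arms.
2. In the safety tables (8.3.4, 9.4.4), beside each lab- or vital-sign-based event rate, show by arm and by pre/post period the tests or BP readings per patient-year and the number and percentage of patients tested. Give percent abnormal as an aid only, since extra tests in lower-risk patients can lower it and mask harm.
3. Use all-cause admissions and ED visits (already listed in 9.4.2.1) and mortality as the between-arm safety anchors. Either define renal admission by principal discharge diagnosis, independent of the problem list, or keep the renal/non-renal split descriptive.
4. Section 10.1.6 names ED or hospital admissions related to syncope, hypotension or hypoglycemia. Add an acute-care-coded version of electrolyte events, which it does not name in that form.

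The cost is wording and extra table columns. BP readings and laboratory values, including electrolytes, are already collected (9.4.5). The acute-care-coded version will have fewer events and so less precision.
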